Potential participants, after signing an informed consent, will be identified based on the following criteria:

- Sustained a concussive injury at least 3 months ago
- The injury did not involve any diagnosed bleeding within the brain
- You did not lose consciousness for longer than 30 minutes
- You have no history of severe migraine headaches prior to the injury
- Were 18 years of age or older at the time of the injury
- Are currently receiving treatment as an outpatient with [name]
- You are not currently receiving IV infusions of medications from a headache specialist at the time of treatment
- You do not have a history of rheumatoid arthritis

The research protocol will be designed in the following way:

- 1. A goal of 15 patients are to be enrolled in the study as well as an equal number of 15 control subjects who will not participate in osteopathic treatments. The selected patients will be seen for a total of three visits of which the first two sessions will be treatment visits. All visits will be in 4 week intervals.
- 2. Patients selected to participate in the study will undergo a musculoskeletal examination of the cervical spine. Testing will be comprised of:

- a. Range of motion testing involving cervical rotation, lateral side bending, flexion and extension.
- b. Muscular palpation of the cervical paraspinals for hypertonicity of the muscles and/or tenderness.
- 3. The patient will then be placed supine on the examination table after which treatment will commence.
- 4. Treatment sessions will last for 5-10 minutes each and will be performed by one osteopathic physician. In the time allotted, three OMT techniques will be performed: cervical muscle energy, myofascial release of the cervical paraspinals and a suboccipital release. The three physicians will have met prior to treatment to standardize protocol.
- 5. Patients will be asked to complete the Headache Impact Test (HIT-6) at visit 1 and 2 between about 6 weeks. All patients will also quantify their pain using a pain scale before and after treatment.
  - 6. Change scores between pain scales between treatments will be assessed, and improvements between HIT-6 scores will be analyzed for statistical significance.

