# Statistical Plan (last update on July 15, 2017)

JMP version 14.1 (SAS Institute Inc) was used for statistical analysis. Descriptive statistics (mean, median, SD) and graphical (box plots, bar charts) methods were used. For the treatment group, a paired Wilcoxon signed rank test was performed to assess the change in VAS data from pretreatment to posttreatment. With 10 patients, we had 89% power to detect a change of 2 in the VAS scores from pretreatment to posttreatment, assuming a 2-sided significance level of 5% and a standard deviation of 2 (effect size =1). The Wilcoxon rank sum test for continuous (eg, age) and discrete (eg. variables (eg, change in HIT-6 scores, time from injury to visit [months]) and the Pearson x2 test for categorical variables (eg, mechanism of injury, history of prior MTBI) were performed for comparison of the treatment and control groups. With 20 patients (10 per group), we had 80% power to detect a difference in the means of 10 between the groups in HIT-6, assuming a standard deviation of 8, and a 2-sided significance level of 5%. Two-sided P value <.05 was considered statistically significant.

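### The stated 89% (VAS) and 80% (HIT-6) power fit a known-variance z formula; under normal data the Wilcoxon tests named give about 79% and 71% at 10 per group, and the protocol enrols 15 per group

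*Combined protocol and SAP*

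**What the plan says.** The Statistical Plan (last update July 15, 2017) gives two power statements, both at a two-sided 5% level.

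- **VAS, treatment group only.** "With 10 patients, we had 89% power to detect a change of 2 in the VAS scores from pretreatment to posttreatment". The SD is 2 and the effect size is given as 1. For the analysis, "a paired Wilcoxon signed rank test was performed to assess the change in VAS data from pretreatment to posttreatment".
- **HIT-6, treatment versus control.** "With 20 patients (10 per group), we had 80% power to detect a difference in the means of 10 between the groups in HIT-6". The SD is 8. Change in HIT-6 is listed among the variables compared by the Wilcoxon rank sum test.

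The plan does not say which test or formula the powers were calculated for.

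The Protocol (last update January 11, 2019), item 1 of the research design list, sets a different size: "A goal of 15 patients are to be enrolled in the study as well as an equal number of 15 control subjects". Neither part contains a dropout allowance, a definition of completers or any other sentence that relates 15 per group to 10 per group.

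**The concern.** With 10 pairs there are 9 degrees of freedom, and with 10 per group there are 18. At these sizes, treating the SD as known makes power look materially better than it is, and rank tests lose a little more when the data are normal. The stated 89% and 80% looked too high for the tests that the plan names.

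The stake is how a null result is read. For a true 10-point HIT-6 difference, 80% power means a 20% chance of missing it. HIT-6 is also the only outcome for which the plan gives a powered between-group comparison. If the true power is lower, a non-significant result is weaker evidence of no effect than the reader is told. The second stake is that the reader cannot tell which sample size the power statement is meant to defend.

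**Working it through.** **Inputs** (Statistical Plan unless noted)

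- VAS: n = 10 pairs, change 2, SD 2, so d = 2/2 = 1. The stated effect size of 1 implies that the SD is that of the paired change.
- HIT-6: 10 per group, difference 10, SD 8, so d = 10/8 = 1.25.
- Two-sided alpha 0.05, critical normal value 1.96.
- Protocol, design item 1: 15 per group.

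**Step 1. Reproduce the stated figures.** With the SD treated as known:

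- VAS: Φ(d√n − 1.96) = Φ(3.162 − 1.96) = Φ(1.202) = 88.5%. Stated: 89%.
- HIT-6: Φ(d√(n/2) − 1.96) = Φ(1.25 × √5 − 1.96) = Φ(2.795 − 1.96) = Φ(0.835) = 79.8%. Stated: 80%.

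Both match after rounding. Other routes were tried. A one-sided t-test gives 89.8% and 85.1%, which fits VAS only. A one-sided exact Wilcoxon test gives 86.4% and 81.6%, which fits HIT-6 only. Both also contradict the stated two-sided level. Scaling n by 3/π in the z formula gives 87.1% and 78.0%, a poorer fit to both. Of the variants tried, the two-sided z formula is the only one that rounds to both stated figures.

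**Step 2. Allow for estimating the SD.** Two-sided t-tests, using the noncentral t distribution:

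- VAS: 9 df, noncentrality 3.162, power 80.3%.
- HIT-6: 18 df, noncentrality 2.795, power 75.3%.

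**Step 3. Use the named tests.** Power was simulated under normal data with exact null critical values (1,000,000 replicates for signed rank, 500,000 for rank sum):

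- Signed rank, n = 10: reject if the smaller rank sum is 8 or less (true size 4.88%); power 78.5%.
- Rank sum, 10 per group: reject if the smaller U is 23 or less (true size 4.33%); power 70.6%.

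**Step 4. Repeat at the protocol's size and compare.**

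| | Stated | z | t | Exact Wilcoxon |
|---|---|---|---|---|
| VAS, n = 10 | 89% | 88.5% | 80.3% | 78.5% |
| HIT-6, 10 per group | 80% | 79.8% | 75.3% | 70.6% |
| VAS, n = 15 | none | 97.2% | 94.9% | 93.8% |
| HIT-6, 15 per group | none | 92.8% | 91.0% | 88.7% |

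At 10 per group the gap is 89 − 78.5 = 10.5 points for VAS and 80 − 70.6 = 9.4 points for HIT-6. The chance of missing the assumed effect is 21.5% rather than 11% for VAS, and 29.4% rather than 20% for HIT-6.

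**Step 5. Sensitivity at n = 10.** Under normal data, the rank sum test by normal approximation without continuity correction gives 73.7%, and the signed rank test with continuity correction gives 73.8%. Rounding scores to integers gives about 78% (VAS) and 72% (HIT-6).

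**The case against.** The strongest reply has four parts.

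1. *The only enrolment target is 15 per group, and there both tests exceed the stated power.* This is true, and it limits the overstatement to the case where 10 per group are analysed. But the plan attaches 89% and 80% expressly to 10 patients and 10 per group, so the statement is wrong at the size it names.

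2. *The 71% for HIT-6 depends on normal data and an exact critical value, neither of which the plan specifies.* This stands in part. With the same difference and SD, t-distributed data with 5 df give about 78% (exact) to 81% (normal approximation), and Laplace data about 79% to 82%. Uniform data go the other way, to about 66% with the exact test. So the stated 80% is reachable under some distributions and test versions, but nothing in the plan supports choosing them. The VAS figure is sturdier: it stayed well below 89% in every case tried, reaching about 81% at best.

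3. *The SDs are round planning values without a source.* Also fair. Under normality, an SD of a little under 7.2 instead of 8 would restore 80% for the exact rank sum test, and the plan does not say whether 8 refers to the HIT-6 score or to its change. That is uncertainty about the input. It does not make the calculation from the plan's own input correct.

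4. *Fifteen is a goal and ten may be the analysed set, since the plan is written in the past tense.* That reading is possible, but no sentence says so.

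**Conclusion.** The point holds. At the sample size the plan itself gives, its power is overstated for the tests it names: about 79% rather than 89% for VAS, and about 71% rather than 80% for HIT-6. Even t-tests on the same inputs miss both figures, so the conclusion does not depend on the loss from using ranks. The sample sizes in the two parts differ (10 against 15 per group) without explanation, and the choice moves exact Wilcoxon power from about 79% and 71% to about 94% and 89%.

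The Wilcoxon figures assume normal data, an SD of 2 for the paired VAS change and an SD of 8 for the HIT-6 quantity compared. The VAS result is robust to the alternatives tried; the HIT-6 result is more sensitive to the distribution. That the stated figures came from a known-variance formula is an inference from the match, since the plan names no method. The validity of the Wilcoxon p-values is not affected.

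**What to change.** - State one sample size per group in both the Protocol and the Statistical Plan. If 10 is meant as completers out of 15 enrolled, say so and give the allowance.
- Restate power for the named tests, with the method and the distributional assumption. Under normal data with exact tests: about 79% (VAS) and 71% (HIT-6) if 10 per group are analysed, or about 94% and 89% if 15 per group are.
- Say whether the SD of 8 is that of the HIT-6 score or of its change.

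The cost is wording only. No test, significance level, visit or number of patients has to change. If 10 per group is kept, the published power becomes less favourable.

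### The between-group HIT-6 comparison leaves out the baseline score that is already collected, which costs some power and yields no adjusted difference in points

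*Combined protocol and SAP*

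**What the plan says.** The Statistical Plan uses the Wilcoxon rank sum test to compare the treated and control groups on age and on "discrete (eg. variables (eg, change in HIT-6 scores, time from injury to visit [months". It names no baseline covariate, adjusted model or sensitivity analysis for HIT-6. The other efficacy test, the signed rank test on VAS, is confined to the treated group, so this is the only between-group efficacy analysis.

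The baseline value exists. Item 5 of the research design in the Protocol states: "Patients will be asked to complete the Headache Impact Test (HIT-6) at visit 1 and 2". Item 6 adds that "improvements between HIT-6 scores will be analyzed for statistical significance", again without mention of adjustment.

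The power statement covers two equal groups of 10. It puts power at 80%, and its stated aim is "to detect a difference in the means of 10 between the groups in HIT-6". The SD is taken as 8 and the test as two-sided at 5%. It does not say whether 8 is the SD of the change or of a single score.

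The design section plans 15 treated patients and 15 untreated controls. It describes no randomisation, matching or stratification.

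**The concern.** A change score fixes the slope of follow-up on baseline at 1. When the true slope is lower, the change carries avoidable noise, and a model that estimates the slope is more precise. With 10 to 15 patients per group, that precision is worth having.

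The power target is a difference in means, but a rank sum test by itself delivers only a P value. The plan asks for no between-group difference in points with an interval.

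There is also a question of bias. If both groups regress towards a common mean, the group that starts higher will tend to fall further without any treatment effect. The plan compares characteristics such as age, time from injury, mechanism and prior injury between the groups, but does not say that any imbalance feeds into the HIT-6 analysis.

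**Working it through.** **Inputs from the Statistical Plan:** 10 per group, difference 10, SD 8, two-sided 5%. **Assumed, because the documents do not give it:** correlation ρ between baseline and follow-up HIT-6 of 0.3, 0.5 or 0.7. The simulations use normal data.

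**1. The plan's own figure.** Standard error = 8 × √(2/10) = 3.58. Power ≈ Φ(10/3.58 − 1.96) = Φ(0.835) = 79.8%. This reproduces the stated 80% as a normal approximation. With the t distribution (18 df), power is 75.3%. The rank sum test, simulated, has about 70-71%.

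**2. Power with baseline adjustment, taking 8 as the SD of change.** Var(change) = 2σ²(1−ρ) and the ANCOVA residual variance is σ²(1−ρ²), so the ratio is (1+ρ)/2. The residual SD is 8 × √((1+ρ)/2). The last three columns are simulated power.

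| ρ | Residual SD | Rank sum on change | t-test on change | ANCOVA |
|---|---|---|---|---|
| 0.3 | 6.45 | 71% | 75-76% | 89% |
| 0.5 | 6.93 | 70-71% | 75% | 84% |
| 0.7 | 7.38 | 71% | 75-76% | 79% |

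ANCOVA against the t-test on change isolates adjustment: about 13, 9 and 4 points. The remaining 4 to 5 points of the gain come from replacing a rank test with a parametric one on normal data.

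At the Protocol's 15 per group, the rank sum test has about 89%, and ANCOVA 98%, 96% and 94%.

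**3. The same, taking 8 as the single-score SD (10 per group).** Rank sum against ANCOVA is about 56-57% v 76-78% at ρ = 0.3, 70-72% v 84% at 0.5, and 90% v 94% at 0.7. The gain is small when ρ is high.

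**4. Baseline imbalance with no treatment effect (single-score SD 8).** Let the treated group's population mean start d = 6 points higher, with ρ = 0.5. Two structures are possible:

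- *Both groups on one regression line.* The change difference shifts by −(1−ρ)d = −0.5 × 6 = −3.0 points. The rank sum test rejects in about 11% of trials at 10 per group and 15% at 15; ANCOVA stays at about 5%.
- *Groups differ stably, each regressing to its own mean.* The change difference is unbiased and the rank sum test rejects in about 4-5%. ANCOVA shows +(1−ρ)d = +3.0 points and rejects in about 13% at 10 per group and 18-19% at 15.

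**5. How usual is a 6-point gap by chance?** The chance SD of the baseline difference is 8 × √(2/10) = 3.6 points at 10 per group and 8 × √(2/15) = 2.9 at 15. A gap of at least 6 in one given direction has probability of about 4.7% and 2.0%. Averaged over chance imbalances, the rank sum test keeps its level (about 4-5%).

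**The case against.** The strongest reply is that the planned test is valid and the adjusted model is not clearly safer. A change score already subtracts the baseline. What remains, (1−ρ)d, is a bias only under a common regression line. Controls are defined as people who will not receive the treatment and no randomisation is described, so stable group differences are quite possible, and under them the recommended model is the one that errs. This stands.

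A reader might infer that any baseline difference between the groups necessarily becomes a false treatment effect, or that ANCOVA would cure it. The documents support neither reading: they do not say how the groups regress, and one covariate does not deal with selection. Nor does chance imbalance inflate the overall error rate of the planned test; the 11% and 15% figures are conditional on a fairly unusual gap.

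It can also be said that rank methods are a reasonable choice for very small groups and that normal simulated data flatter ANCOVA. That is fair. It is why the gain is split above, and why a rank-based ANCOVA is an acceptable alternative.

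None of this removes the efficiency point. ANCOVA was ahead at every correlation tried, under either meaning of the SD, and the baseline scores cost nothing more to use.

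**Conclusion.** The concern holds as a minor point of efficiency and reporting. The plan's only between-group efficacy test ignores a baseline score that is collected, and produces no adjusted difference with an interval. At 10 per group, with 8 as the SD of change and ρ between 0.3 and 0.7, the planned test falls about 9 to 18 points of power short of ANCOVA, of which about 4 to 13 are due to adjustment. With 8 as the single-score SD, the total shortfall runs from about 4 points (ρ = 0.7) to about 21 (ρ = 0.3).

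These sizes rest on normal data and on a correlation that the documents do not give. Bias from baseline imbalance is a possibility under one structure, not a demonstrated defect, and the direction of the problem reverses under the other.

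**What to change.** In the Statistical Plan, add a prespecified linear model of follow-up HIT-6 on group and visit 1 HIT-6, or a rank ANCOVA if the data are clearly non-normal. For the linear model, report the adjusted difference in points with its 95% CI. Keep the rank sum test on change beside it, and say how a disagreement between the two will be interpreted, since it would bear on which regression structure applies. State that neither analysis removes confounding from groups that were not randomised. State also whether the SD of 8 refers to change or to a single score.

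The Statistical Plan is written in the past tense. If the analysis is already complete, the model can still be added but should be labelled post hoc.

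The cost is one model and one degree of freedom, with no new data, visits or patients. The downsides are a linear-model assumption in small groups and dependence on the common-regression assumption.

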Patients who do not recover after three months after a mTBI are categorized as having post concussive syndrome (PCS), which affects approximately 15% of patients [6,7]. A longitudinal study assessing 285 patients with PCS found that 27% of the population studied eventually recovered and 67% of those who recovered did so within the first year [8]. In this study, no patient recovered who had PCS lasting 3 years or longer. Symptoms included persistent headaches and depression. Guidelines for management of PCS have not been completely established, and patients are generally recommended to continue physical and cognitive rest.

Osteopathic Manipulative Therapy (OMT) is a nonpharmacological, noninvasive form of manual medicine. Osteopathic practitioners use a wide variety of therapeutic manual techniques to improve physiological function and help restore homeostasis in the body. There is a structural assessment is to identify possible abnormalities of tissue texture. Areas of asymmetry and misalignment of bony landmarks are also evaluated, along with the quality of motion, balance, and organization. These asymmetries, also known as somatic dysfunctions, are then treated by a variety of manual treatments, administered by osteopaths [10].

There has been research showing the effectiveness of OMT in the treatment of various types of headaches. A recent systematic review assessed 6 studies with various

types of headaches including tension-type headaches, migraine headache, all which showed statistically significant changes in various outcome measures. Outcome measures included the Headache Impact Test (HIT-6) score, headache pain intensity / frequency, and HRQoL [10]. A randomized control trial studied 62 patients with tension-type headaches, and showed that manual therapy techniques to the suboccipital region offered a positive improvement in some aspects of the patient's quality of life [11]. Another systematic review assessing migraine type headaches showed a preliminary low level of evidence that OMT is effective in the management of headache [12]. Overall, studies concluded that more rigorous designs and methodology are needed to strengthen the evidence that OMT has benefit in headache management.

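### Time since injury, which the protocol links to recovery, is used only in a low-power baseline test while HIT-6 change is compared without it; a systematic difference in chronicity could bias that comparison either way

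*Combined protocol and SAP*

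**What the plan says.** - **Natural course (Protocol, background).** A cited cohort of 285 patients with post-concussive syndrome (PCS) found that "27% of the population studied eventually recovered and 67% of those who recovered did so within the first year". In the same cohort, "no patient recovered who had PCS lasting 3 years or longer".
- **Eligibility (Protocol, criteria list).** The only condition on chronicity is a minimum: "Sustained a concussive injury at least 3 months ago". No maximum is listed.
- **Controls (Protocol, design item 1).** The treated patients are set beside a comparison group: "as well as an equal number of 15 control subjects who will not participate in osteopathic treatments". Randomisation, matching and stratification are not described.
- **Analysis (Statistical Plan).** Time from injury appears once, as an example of a variable compared between groups by Wilcoxon rank sum test: "eg, change in HIT-6 scores, time from injury to visit [months". HIT-6 change is compared by the same test. No covariate-adjusted or stratified analysis is named.
- **Design figures (Statistical Plan).** The HIT-6 power statement takes 10 per group, a difference of 10, an SD of 8 and a two-sided 5% level, and claims 80% power.

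**The concern.** The trial collects a variable that its own background associates with recovery, checks it for balance, and then leaves it out of the outcome comparison. With only a lower limit on chronicity, a patient at 4 months and a patient at 5 years count as exchangeable in the HIT-6 test, although the cited cohort suggests different expected courses.

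The design as described does nothing to keep the groups alike on this variable. If the controls were more chronic, spontaneous improvement in the treated group would count towards osteopathic manipulative therapy (OMT). If they were less chronic, it would mask an effect. A reader who asks whether the controls simply had older injuries would get only a baseline P value, and at this size a non-significant one does not show that the groups are comparable.

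**Working it through.** **Inputs.** From the Statistical Plan: 10 per group, HIT-6 difference 10, SD 8, two-sided 5%. From the protocol: 15 per group, 27% recovered, 67% of those in the first year, none at 3 years or longer. *Assumed, because the documents give neither:* the correlation r between log time since injury and HIT-6 change, and the imbalance d between groups in SD units.

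**1. The plan's own power figure.** Normal approximation: 10 / (8 × √(2/10)) = 2.795; 2.795 − 1.960 = 0.835; Φ(0.835) = 79.8%. The stated 80% reproduces. A two-sample t test gives 75%, and the planned rank sum test about 71% (simulated, normal data).

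**2. Power of the baseline comparison of time since injury** (rank sum, simulated):

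| Imbalance d | 10 per group | 15 per group |
|---|---|---|
| 0.5 SD | 16% | 24% |
| 0.8 SD | 35% | 53% |
| 1.0 SD | 51% | 72% |

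**3. Size implied by the protocol's recovery figures.**
- Recovered in the first year: 0.27 × 0.67 = 18.1% of all patients. Recovered later: 0.27 × 0.33 = 8.9%.
- Probability of recovering over an interval of w weeks, with the 18.1% spread over m months: 1 − (1 − 0.181)^(w / 4.345 / m). The protocol gives both 4-week visits and about 6 weeks between HIT-6 assessments, so w is taken from 4 to 8, and m as 9 or 12.
- Lowest: w = 4, m = 12 gives 1.5%. Highest: w = 8, m = 9 gives 4.0%.
- Assume a drop of 10 to 30 HIT-6 points per recovered patient, and complete separation (all treated patients in year 1, all controls beyond 3 years). The shift in means runs from 0.0152 × 10 ≈ 0.2 to 0.040 × 30 = 1.2 points.
- With half the patients early, half late and SD 8, that is a correlation of (0.2/2)/8 ≈ 0.01 to (1.2/2)/8 ≈ 0.08.

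**4. Bias and error rate over a range of r at d = 1.** Bias = 8 × r × d. False-positive rates are for the unadjusted rank sum test with no OMT effect.

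| r | Bias (points) | 10 per group | 15 per group |
|---|---|---|---|
| 0.05 | 0.4 | about 4% | about 4% |
| 0.3 | 2.4 | about 8% | about 12% |
| 0.5 | 4.0 | about 15% | about 23% |

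These are simulated, and repeated runs differ by about one percentage point. The adjusted linear model stays near 5% throughout, but the data were generated linear in log time, so it is favoured by construction.

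**5. The opposite direction.** At 10 per group, r = 0.3 and d = 0.8, the bias is 8 × 0.3 × 0.8 = 1.9 points. If it opposes a true 10-point effect, rank sum power falls from about 71% to 52%, and the baseline test misses the imbalance about 65% of the time.

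**6. Cost of adjusting.** At 10 per group and d = 1, the adjusted model has about 64 to 67% power for 10 points when r is 0.05 to 0.3. With balanced groups and r = 0.3 it has about 76%, against 75% for the unadjusted t test.

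**The case against.** The strongest objection is about size. The recovery figures that motivate the concern imply at most about 1.2 HIT-6 points, even under complete separation, and a correlation below 0.1. At r of 0.05 to 0.1 the false-positive rate at 10 per group stays at about 4 to 5%, and adjustment gains nothing. Larger bias requires graded improvement that also depends on chronicity. That is plausible for a graded score, but the documents do not quantify it. **This stands**, and it is why the size must be given as a range that starts near zero.

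A reader might also infer some stronger points that the documents do not support:

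- *That the protocol says time since injury determines recovery.* It reports an association in one cohort, for recovery from PCS, not for HIT-6 change over a few weeks.
- *That chance imbalance alone inflates the error rate.* The rates in step 4 assume a fixed 1 SD shift, that is, systematic selection. Under random assignment the probability of an imbalance of 1 SD or more would be about 2.5% at 10 per group (1/√(2/10) = 2.24) and 0.6% at 15 (1/√(2/15) = 2.74), and the unadjusted test would keep its overall 5% level.
- *That the covariate gives a clear power gain in balanced groups.* Nearly all of the rise from 71% to about 76% at r = 0.3 comes from leaving the rank test.
- *That the lack of an upper limit is itself an error.* The 3-month floor agrees with the protocol's definition of PCS. Whether to set a ceiling is an eligibility decision for the sponsor.

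It is also fair to say that the root problem is how controls are chosen, and that one covariate does not cure it. That does not justify leaving a collected prognostic variable out of the analysis.

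**Conclusion.** The point holds as a weakness in the analysis plan that should be corrected. The documents establish that recovery is associated with time since injury, that nothing described protects balance on it, and that the HIT-6 comparison ignores it. A systematic difference in chronicity could bias that comparison in either direction, and the planned baseline test would miss a 1 SD difference about half the time at 10 per group.

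The size is not established. It lies between about 0.2 to 1.2 points (full recovery only, at the protocol's rates, with an assumed 10 to 30 point drop) and 0.4 to 4 points (assumed r of 0.05 to 0.5 with an assumed 1 SD imbalance). The corresponding false-positive rates for the second range are about 4 to 15% at 10 per group and 4 to 23% at 15. A reader might infer that natural recovery could by itself produce the 10-point design difference; none of these figures supports that.

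**What to change.** In the Statistical Plan:

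1. Specify a linear model of HIT-6 change with group and log(months since injury) as terms. Fit it whatever the baseline comparison shows, and report the adjusted group difference with its confidence interval beside the rank sum result.
2. State that a non-significant baseline test of time since injury will not be read as evidence that the groups are comparable; describe the variable by group instead.
3. The plan is written in the past tense. If outcome data have already been seen, label the adjusted analysis as added later.

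**Cost.** A short addition to the plan, using a variable already collected, and one degree of freedom. When groups are imbalanced the interval widens, with the power loss shown in step 6. The model also relies on approximate linearity in log months, which the cited cohort does not establish and which should be checked on a plot. A listing by bands of chronicity within group is not recommended: three bands by two groups would leave about 20/6 ≈ 3 patients per cell at 20 patients, or 30/6 = 5 at 30.
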